2.0 Objectives*

2.1 Primary Objectives:

1. Measure physical activity and sleep for up to 365 (\pm 30 days) days using a Garmin physical activity tracker among youth and young adults with T1D.
2. Evaluate the impact of physical activity and sleep related variables on rate of DKA admission over 90 and 180, and 365 \pm 30 days
3. Evaluate the impact of physical activity and sleep related variables on change in Time in Range and other continuous glucose monitor-derived metrics of glycemic control over 90, 180, and 365 \pm 30 days
4. Test the impact of physical activity and sleep related variables on machine learning models to predict change in HbA1c, DKA admissions, and change in Time in Range over 90, 180 and 365 \pm 30 days

2.2 Secondary Objectives:

1. Examine for correlations between self-reported physical activity (IPAQ), hypoglycemia fear (HFS-II), and parent hypoglycemia fear (HFS-P) at 0, 6, and 12 months after study enrollment.
2. Evaluate any change in physical activity levels via self-report with the IPAQ survey (to allow comparisons to external cohorts).
3. Evaluate any change in how participants feel about episodes of hypoglycemia while wearing the Garmin physical activity tracker via the Hypoglycemic Fear Scale II (HFS-II)
4. Evaluate any change in how parents feel about episodes of hypoglycemia in their children wearing the Garmin physical activity tracker via the Hypoglycemic Fear Scale II for Parents (HFS-P)

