4.0 Study Endpoints

1. Minutes/day of Moderate-to-vigorous physical activity (MVPA) – from Garmin device over 30, 90, 180, and 365 ± 30 days
2. Sleep minutes/day – derived from Garmin device over 30, 90, 180, and 365 ± 30 days
3. Other activity metrics derived from Garmin device over 30, 90, 180, and 365 ± 30 days
4. HbA1c – collected from Electronic Medical Record, obtained via standard care (binned as 46-135 days, 136-225 days, 226-305 days, and 306-410 days)
5. Hospital admissions for DKA (0-180 days and $181-365 \pm 30$ days)
6. 14-day Time in Range and other CGM-derived metrics of the quality of glycemic control over 30, 90, 180, and 365 ± 30 days
7. Model performance characteristics (e.g. precision, recall, F1) of predictive models for the outcomes listed in 4.1-4.6

5.0 Study Design*Participants with T1D treated at the Children's Mercy Endocrine clinic aged 8-21 years old will be asked to wear a Garmin VivoSmart 4 (or later) physical activity tracker for at least 6 months. This tracker will collect detailed physical activity and sleep data as measured by moderate to vigorous physical activity (MVPA) and sleep minutes/day. The tracker collects heart rate and accelerometry data, collected into the Garmin Connect application. The diabetes center will use the Garmin Health API connection developed by Children's Mercy Research Informatics to extract the data into a data warehouse in Microsoft Azure (CMH account). As noted in previous studies, MVPA is automatically measured by the tracker when the wearer runs for >1 minute or walks for >10 consecutive minutes. The weekly MVPA and step count are both weighted by multiplying the mean of weekday activity by 5, adding it to the mean of weekend activity and dividing the sum by 7.

$$\text{Weighted MVPA} = \frac{[(\text{MVPA}) \times 5] + (\text{MWVPA})}{7}$$

$$\text{Weighted step count} = \frac{[(\text{MSC}) \times 5] + (\text{MSC weekend})}{7}$$

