If the subject wears the tracker for >8 hours between 9 AM and 9 PM, the day is used in the weighing calculation (Grimes et al., 2022). Clinical data will be collected from the medical record and coded (labeled with the study ID to minimize use of personal data). Also, self-reported personal health will be collected from the CMH-approved vendor software to which they upload their self-management device data. Baseline and end of study surveys including International Physical Activity Questionnaire (IPAQ), the Hypoglycemic Fear Scale II (HFS-II) for participants, and Hypoglycemic Fear Scale for parents (HFS-P) will be collected from participants/ parents. Surveys will be given to participants based on their ages and the ages surveys are validated for.

Table of Events:

	Pre-screening (Pre-consent)	Visit 1 Day 1 app x.	Visit 2 ^a Day 14 appx. (PRN)	Visit 3 ^a Day 28 appx. (PRN)	Visit 4 ^a Day 56 appx. (PRN)	Visit 5 Day 180 appx.	Visit 6 Day 365 appx.	Unscheduled Visit
EMR Review Eligibility	X							
Verbal Consent		X						
Demographics		X						
Clinical history ^b		X					X	
Send Garmin tracker		X						
Surveys ^c		X				X	X	
Mid-Study Check-In Survey						X		
Garmin Troubleshooting Visits			X	X	X			

- a. Additional virtual or in person visits may be scheduled at Visit 2, Visit 3, and Visit 4 as needed for device troubleshooting and additional education, depending on the needs of the subjects
- b. A1c will be drawn SOC as a part of the clinical history, in the absence of A1c results, GMI will be deduced from CGM data
- c. The IPAQ (for >15 YO) and HFS-P/HFS-II (HFS-II child for 11-18 Y.O., HFS-II adult for >18 YO)

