9.2 Pre-Screening prior to HIPAA Authorization

Will any of the identification methods checked above involve access to Protected Health Information (PHI) prior to obtaining HIPAA Authorization?

- Yes

SHORT TITLE:

No

- *If yes, a “Partial Waiver of HIPAA Authorization” is required. Be sure to make this selection in the “HIPAA & Confidentiality” section below and complete [Addendum E: Waiver/Alteration of HIPAA Authorization](#)*

9.3 Recruitment of Potential Participants:

Participants will be recruited from the CMH diabetes clinic, at diabetes events CM participates in (such as T1D walks or camps), by identifying youth 8-21 Y.O. with T1D who have a predicted rise in HbA1c of 0.3 points, by CM approved electronic communication (emails or texts- including the Health Device Portal Messaging) or by physician referral to the study. Flyers describing the study generally (discussing who researchers are looking for, what they would have to do, and receiving the Garmin devices) will be posted in the diabetes clinic, CM study lists (I.e. Find a Study, the clinic intake form), and at T1D events. Also, the flyer/ link to the flyer can be sent to T1D patients via email (via CM approved email servers)/ text (CM approved SMS servers including the Health Device portal messaging). The flyers will contain the study coordinator and PI contact information so the participant can reach out for information/ screening. After the initial screening to confirm eligibility, participants will be contacted via telephone and asked if they want to be emailed the consent letter to obtain verbal consent. Participants will be called up to three times, and all visits will be virtual unless a participant requests to be in person, if so the study visit will be coordinated with their standard of care clinical visit.

10.0 Surveys and Psychometric Testing:

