26.0 Data Collection*

This study will be completely integrated into the Diabetes Data Dock at CMKC. Data will be collected and paired with the other wearable devices, such as pump and continuous glucose monitor readings.

SHORT TITLE:

Surveys (IPAQ, HFS-II/P) will be collected at baseline and EOS. Data collected from EMR will include medical history, lab results, demographics, clinical data, insurance type (public vs private).

Child/ adult participant data -

Demographic data: We will use the REDCap demographics survey to collect demographic data. We may use the Diabetes Data Dock and/or the child's electronic health record to verify or extend demographic data (e.g., T1D diagnosis, history of T1D-related complications, T1D regimen, shipping address to send the Garmin Device, shipping history).

HbA1c data: We will use routine T1D care POC HbA1c levels to at baseline and at post-treatment (~3 months post baseline).

CGM or SMBG data: Families will use their personal, prescribed CGM or standard blood glucose monitor (SMBG) throughout the study. Families will share CGM data with the study team using their personal, CM connected account. Data will be download automatically to the Diabetes Data Dock using API.

Insulin delivery data: Participants will use their personal, prescribed insulin delivery device throughout the study. Participants and parents/LARs of adolescents will share participants' insulin device data with the study team using their personal, CM connected account.

Questionnaire data: We will use REDCap to electronically collect any survey data, including participants' daily activity schedules. We will use a single REDCap database for all study participants. This REDCap data base will reside on a CM secured server.

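### Footnote b fills a missing HbA1c with CGM-derived GMI, endpoint 4 does not, and no rule keeps the two measures apart in the HbA1c change score

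*Combined protocol and SAP*

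**What the plan says.** Primary Objective 4 (Section 2.1) tests "machine learning models to predict change in HbA1c, DKA admissions, and change in Time in Range over 90, 180 and 365" ± 30 days.

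The plan describes the HbA1c value behind that objective in three places:

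- **Section 4.0, endpoint 4:** HbA1c is "collected from Electronic Medical Record, obtained via standard care", in four follow-up bins from day 46 to day 410. GMI is not mentioned.
- **Section 26.0, HbA1c data:** "We will use routine T1D care POC HbA1c levels to at baseline and at post-treatment (~3 months post baseline"). GMI is not mentioned.
- **Section 5.0, Table of Events, footnote b:** "in the absence of A1c results, GMI will be deduced from CGM data". The footnote is attached to the clinical-history row, which is marked at Visit 1 (day 1) and Visit 6 (day 365) only.

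Section 26.0 also sets out who can have a GMI: "Families will use their personal, prescribed CGM or standard blood glucose monitor (SMBG) throughout the study". Endpoint 6 lists Time in Range together with other CGM-derived metrics.

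Section 28.0 covers only propensity-score matching, and both baseline HbA1c and time in range are among the matching variables. No section requires the same measure at both ends of a change score, flags a GMI-filled value, sets a CGM window or minimum wear for GMI, or plans an analysis without GMI-filled values.

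**The concern.** HbA1c is a blood measurement, and GMI is deduced from sensor glucose. If one end of a change score is HbA1c and the other is GMI, the result is the true change plus that person's difference between the two measures. In a like-for-like pair the stable part of that difference cancels. In a mixed pair it stays in full. It can look like a rise, look like a fall, or mask a real change.

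Three features of this plan make the problem more than a technicality:

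1. **Baseline.** The footnote covers Visit 1. A GMI-filled baseline would enter the change score at every horizon where follow-up is a measured HbA1c. It could also enter the propensity score as baseline HbA1c.
2. **Device use.** Only CGM users can be filled. Substitution is therefore tied to device use and to lacking a routine HbA1c result, and is unlikely to be random.
3. **Overlap of outcomes.** GMI and Time in Range come from the same CGM data. Filled values make two outcomes that Primary Objective 4 lists separately partly the same measurement. A filled baseline would do the same to two of the matching variables.

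**Working it through.** **No figure to reproduce.** The documents give no SD, effect size, power calculation, missing-HbA1c rate or HbA1c-GMI agreement. What follows is an illustration, not an estimate.

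**Inputs from the documents**
- Yardstick of 0.3 points. Section 9.3 names youth with a "predicted rise in HbA1c of 0.3 points" as one recruitment route. It is the only HbA1c change the documents single out, and it is not an endpoint threshold.
- 200 youth (Sections 1 and 8.0).

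**Assumed inputs**
- b, the mean between-measure difference in the order subtracted: 0, +0.2 or -0.2 points.
- s, the SD of that difference: 0.2 to 0.5 points.
- f, the share of youth with a mixed pair: 10% to 30%.

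**Step 1: apparent rise in a mixed pair with no true change.** The apparent change is D ~ Normal(b, s), so

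P(rise ≥ 0.3) = 1 - Φ((0.3 - b)/s).

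For example, b = 0 and s = 0.3 gives 1 - Φ(1.0) = 15.9%.

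| b | s = 0.2 | s = 0.3 | s = 0.4 | s = 0.5 |
|---|---|---|---|---|
| 0 | 6.7% | 15.9% | 22.7% | 27.4% |
| +0.2 | 30.9% | 36.9% | 40.1% | 42.1% |
| -0.2 | 0.6% | 4.8% | 10.6% | 15.9% |

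If GMI is at baseline and HbA1c at follow-up, the sign of b reverses and the last two rows change places.

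**Step 2: change in either direction.**

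P(|change| ≥ 0.3) = 1 - Φ((0.3 - b)/s) + Φ((-0.3 - b)/s).

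At b = 0 this is 13.4%, 31.7%, 45.3% and 54.9% for s = 0.2, 0.3, 0.4 and 0.5.

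**Step 3: a real change hidden.** With a true rise of 0.3 and b = 0, the score shows no rise or a fall with probability Φ((0 - 0.3)/s). By symmetry this equals the first row of the table, 6.7% to 27.4%.

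**Step 4: study level.** Expected false rises of 0.3 or more at b = 0 are 200 × f × P. The low end is 200 × 0.1 × 0.067 = 1.3 youth (s = 0.2), and the high end is 200 × 0.3 × 0.274 = about 16 youth (s = 0.5). The group mean change shifts by f × b, for example 0.3 × 0.2 = 0.06 points.

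**Step 5: after a like-for-like rule.** Where a person's offset is stable, it cancels and the error from switching measure disappears. Ordinary repeat-measurement error remains, and the documents do not allow it to be sized. The percentages above are therefore not purely the excess over a like-for-like pair.

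**The case against.** The strongest objection is that the plan never says GMI enters the HbA1c change score. The footnote says GMI will be deduced, and stops there. Endpoint 4 and Section 26.0 read as measured HbA1c only, and GMI fits naturally among the other CGM metrics in endpoint 6. On that reading there is no mixing rule, only a loose footnote. The objection is right that mixing is permitted and not prescribed. It does not dispose of the point, because the natural sense of a footnote about absent A1c results is substitution. An analyst could follow either section and claim to be following the plan.

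The other objections narrow the point:

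- **Horizons.** A reader might infer that GMI fills gaps at 90 and 180 days. The footnote is attached only to Visits 1 and 6, so follow-up values at those horizons are not directly covered. A filled baseline would still reach them.
- **Frequency.** The endpoint 4 bins are contiguous and 80 to 105 days wide, so any routine HbA1c in a wide window counts. Mixed pairs may be few, and no rate is given.
- **Yardstick.** A reader might take 0.3 points as the plan's meaningful change. It is a recruitment criterion and is not described that way.
- **Model behaviour.** A reader might infer that the model would learn a missed HbA1c as a predictor. No model specification or feature list is given, so this is possible but not shown.
- **Selection.** Restricting to measured pairs drops a group that is probably not random, and so trades measurement error for selection. That is a real cost.

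**Conclusion.** The point holds as an unresolved definition of an outcome in a primary objective. Footnote b states a substitution, endpoint 4 and Section 26.0 do not, and nothing requires like-for-like pairs. The confidence is in the inconsistency and in the arithmetic of a mixed pair, not in the size of the effect.

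The size cannot be determined from the documents. The illustrated ranges depend on the assumed offset, SD and share of mixed pairs, and the rates in steps 1 to 3 describe mixed pairs only, not all 200 youth.

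A reader might conclude that the plan inflates HbA1c rises. The documents do not support that: the direction depends on an offset they do not give, and on which end is filled.

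**What to change.** Reconcile footnote b with endpoint 4 using wording such as:

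> Change in HbA1c is calculated only from measured HbA1c at both time points. Change in GMI is a separate CGM metric under endpoint 6 and is calculated only from GMI at both time points. The two measures are never combined in one change score.

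Apply the same rule to baseline HbA1c in the propensity score (Section 28.1), so that a GMI does not fill it. State the CGM window and minimum wear needed for a GMI, and flag any GMI recorded because an HbA1c was absent.

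The cost is a revised footnote, a line each in Sections 4.0 and 28.1, and no new data collection. The downside is that fewer participants will have an HbA1c change score, and those dropped may differ systematically from those kept. To make that visible, report at each horizon how many lack a measured pair, and present GMI-to-GMI change as a labelled sensitivity analysis. That recovers CGM users with data at both ends. It does not recover participants who use only a standard glucose meter.

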Primary Objectives	
Measure physical activity and sleep for up to 365 days using a Garmin physical activity tracker among youth and young adults with T1D.
 
Evaluate the impact of physical activity and sleep related variables on rate of DKA admission over 90 and 180, and 365 ± 30 days
 
Evaluate the impact of physical activity and sleep related variables on change in Time in Range (TIR) and other continuous glucose monitor-derived metrics of glycemic control over 90, 180, and 365 ± 30 days
 
Test the impact of physical activity and sleep related variables on machine learning models to predict change in HbA1c, DKA admissions, and change in Time in Range over 90, 180, and 365 ± 30 days

Secondary Objectives	
Examine for correlations between self-reported physical activity (IPAQ), hypoglycemia fear (HFS-II), and parent hypoglycemia fear (HFS-P) at 0, 6, and 12 months after study enrollment.
 
Evaluate any change in physical activity levels via self-report with the IPAQ survey (to allow comparisons to external cohorts).
 
Evaluate any change in how participants feel about episodes of hypoglycemia while wearing the Garmin physical activity tracker via the Hypoglycemic Fear Scale II (HFS-II)
 
Evaluate any change in how parents feel about episodes of hypoglycemia in their children wearing the Garmin physical activity tracker via the Hypoglycemic Fear Scale II for Parents (HFS-P)

Research Intervention(s)/	Garmin physical activity tracker

Investigational Agent(s)	
IND/IDE #	NA
Study Population	Youth (8-21 YO) diagnosed with T1D and parents of youth (8-17 YO)
Sample Size	1000 pre-screened for total enrollment goal of 300 (200 youth 100 parents)
Study Duration for Individual Participants	365 Days (\pm 30 days)
Study Specific Abbreviations/ Definitions	T1D = Type 1 diabetes DKA= Diabetic Ketoacidosis IPAQ=International Physical Activity Questionnaire HFS-II=Hypoglycemic Fear Scale II HFS-P= Hypoglycemic Fear Scale II for Parents HbA1c= Hemoglobin A1c

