7.0 Inclusion and Exclusion Criteria*

7.1 Inclusion Criteria

- Participants aged 8-21 years of age and/or parent of participant aged 8-17 years of age
- Participants diagnosed with T1D greater than 6 months ago
- Participants must be patients at the Children's Mercy Kansas City network

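### In Objective 2.2(1), the IPAQ by HFS-P correlation can be computed only at about ages 16-17; a Garmin MVPA by HFS-P correlation, added alongside it, would cover all parent-eligible ages 8-17

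*Combined protocol and SAP*

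**What the plan says.** Objective 2.2(1) reads: "Examine for correlations between self-reported physical activity (IPAQ), hypoglycemia fear (HFS-II), and parent hypoglycemia fear (HFS-P) at 0, 6, and 12 months". Three measures give three pairwise correlations, and the objective sets no age limit on any of them.

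The age limits stand elsewhere:

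- **IPAQ and HFS-II.** Section 5.0, Table of Events, footnote c: "The IPAQ (for >15 YO) and HFS-P/HFS-II (HFS-II child for 11-18 Y.O., HFS-II adult for >18 YO". The body of Section 5.0 gives the reason: "Surveys will be given to participants based on their ages and the ages surveys are validated for".
- **HFS-P.** Footnote c sets no age limit for it. The limit comes from eligibility in Section 7.1: "Participants aged 8-21 years of age and/or parent of participant aged 8-17 years of age". The Study Summary repeats it.
- **Garmin.** Section 5.0 says that clinic patients "aged 8-21 years old will be asked to wear a Garmin VivoSmart 4 (or later) physical activity tracker for at least 6 months". MVPA in minutes/day is the first endpoint in Section 4.0.

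The enrolment goal in Section 8.0 is 200 youth and 100 parents. The text available for this review ends at Section 28.1, which covers propensity-score matching and does not mention these correlations.

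**The concern.** Each age limit is reasonable alone, but the IPAQ starts near the top of the age range for which parents are enrolled. The correlation of activity with parental fear therefore rests on the oldest minors, and nothing in the objective warns the analyst or reader of this. A coefficient reported for that pair could be read as describing parents of children aged 8-17 when it describes only about two year-ages, and it would probably be too imprecise to interpret. The study meanwhile collects a device measure of activity in every enrolled youth, including those too young for the IPAQ, and Objective 2.2(1) does not use it.

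**Working it through.** The plan gives no number of pairs, precision or power for these correlations, so there is no stated figure to reproduce.

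**Step 1: age overlap, in whole years.** Youth are 8-21 (14 year-ages); children of eligible parents are 8-17 (10 year-ages); IPAQ is 16-21; HFS-II is 11-21 (child and adult forms together).

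| Pair | Ages available |
|---|---|
| IPAQ by HFS-P | 16-17 (2 of the 10 parent-eligible ages) |
| IPAQ by HFS-II | 16-21 (6 of 14 youth ages) |
| HFS-II by HFS-P | 11-17 (7 of 10) |
| Garmin MVPA by HFS-P (not planned) | 8-17 (10 of 10) |
| Garmin MVPA by HFS-II (not planned) | 11-21 (11 of 14) |

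If the IPAQ limit means any age past the 15th birthday, the first row becomes 15-17 (3 of 10). Children aged 8-10 have neither IPAQ nor HFS-II, so their parents' HFS-P scores have no partner in any of the three planned correlations.

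**Step 2: number of pairs.** Assumptions: ages spread evenly, every enrolled parent paired with an enrolled child, all data complete.

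- IPAQ by HFS-P: 100 x 2/10 = 20, or 100 x 3/10 = 30
- HFS-II by HFS-P: 100 x 7/10 = 70
- IPAQ by HFS-II: 200 x 6/14 = 86
- Garmin by HFS-P: 100 x 10/10 = 100
- Garmin by HFS-II: 200 x 11/14 = 157

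**Step 3: precision at an assumed r = 0.30.** Fisher interval: tanh(atanh(0.30) ± 1.96/√(n − 3)), with atanh(0.30) = 0.3095.

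| n | 1.96/√(n − 3) | 95% interval |
|---|---|---|
| 20 | 0.475 | -0.16 to 0.66 |
| 30 | 0.377 | -0.07 to 0.60 |
| 70 | 0.239 | 0.07 to 0.50 |
| 86 | 0.215 | 0.09 to 0.48 |
| 100 | 0.199 | 0.11 to 0.47 |
| 157 | 0.158 | 0.15 to 0.44 |

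**Step 4: the same in terms of power** (two-sided 0.05, assumed). The smallest r detectable with 80% power is tanh((1.96 + 0.84)/√(n − 3)): 0.59 at n = 20, 0.49 at n = 30 and 0.28 at n = 100. Power for r = 0.30 is about 25%, 36% and 86%.

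**Step 5: is the weighted MVPA usable as it stands?** Section 5.0 multiplies the weekday mean by 5, adds the weekend mean once and divides by 7. A child with 30 minutes every day would score (30 x 5 + 30)/7 = 180/7 = 25.7, not 30. If the weekend term is a mean, as the text says, its weight and the divisor do not agree.

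**The case against.** The strongest reply is about scope. Only one of the three correlations shrinks to a narrow age band. IPAQ by HFS-II keeps about 86 youth on the even-age assumption, which is workable, and HFS-II by HFS-P runs over ages 11-17. A reader might infer that Objective 2.2(1) as a whole fails, or that parents of younger children drop out of the study of parental fear. The documents support neither: Objective 2.2(4) evaluates change in HFS-P with no such age restriction, so these parents still contribute there.

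The second reply is that the age cut is deliberate and the objective asks about self-reported activity. Objective 2.2(2) gives comparison with external cohorts as the reason for the IPAQ. A reader might conclude that Garmin MVPA should replace the IPAQ as the main activity measure. That would substitute a different construct, and for HFS-II it would gain only modest precision (0.15 to 0.44 against 0.09 to 0.48). An added analysis is justified; demoting the IPAQ is not.

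Third, Garmin data cannot supply a pre-device baseline. The tracker is shipped after verbal consent (Section 6.4), and it prompts activity and sets goals (Sections 6.1 and 6.2). The Day 1 IPAQ is the scheduled activity measure that precedes wear. This stands and governs how the first Garmin window must be labelled.

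Fourth, the pair counts are illustrative. The age mix is unknown, and the inclusion wording lets a parent or a youth enrol without the other, so 100 complete dyads is an upper bound and not a documented number. Some children aged 15 at entry reach IPAQ age by month 6 or 12, and the documents do not say whether HFS-P continues once a child turns 18, so the later windows may shift slightly. None of this restores the missing younger ages.

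Last, because the available text ends at Section 28.1, it cannot be asserted that no Garmin-by-fear analysis exists elsewhere. What can be said is that Objective 2.2(1) does not include one.

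**Conclusion.** The point holds for one correlation. IPAQ by HFS-P is available only at about ages 16-17 (15-17 on the looser reading), that is 2 or 3 of the 10 parent-eligible year-ages, and parents of children aged 8-10 enter none of the three planned correlations. The age overlap follows directly from the documents. The size of the loss, about 20 to 30 pairs instead of up to 100, rests on even ages and 100 complete dyads; a different age mix would move it either way, and incomplete dyads would lower it. At r = 0.30 the interval includes zero with 20 or 30 pairs and excludes it with 100. This is one part of a secondary, exploratory objective with no stated test, so it calls for a cheap improvement and threatens no primary objective.

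**What to change.** 1. Keep the IPAQ correlations as planned. For IPAQ by HFS-P, state the age range and the expected number of pairs in the plan, and report the observed number with the result.
2. Add to Objective 2.2(1) a prespecified correlation of Garmin MVPA minutes/day (the first endpoint in Section 4.0) with HFS-P for ages 8-17. A matching correlation with HFS-II for ages 11-21 is optional.
3. Fix the windows: the first 30 days of wear for the Day 1 survey, labelled as early post-device activity and not as a pre-device baseline; then the 30 days before the Day 180 and Day 365 surveys.
4. Do not use the weighted MVPA formula in Section 5.0 until its weekend weight is reconciled with the divisor of 7.

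Cost: an amendment to the objective and the analysis text, two trailing 30-day derivations that Section 4.0 does not spell out, and a few more coefficients to report. No visit, survey or participant burden is added. Device MVPA and self-report are different constructs, so both must be shown. Days that miss the wear criterion in Section 5.0 will reduce the number of pairs below 100.
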